5.4.2 Secondary Efficacy Analyses

If the primary endpoint is statistically significant then the 3 key secondary efficacy endpoints will proceed in a sequential manner.

Median percent change in total seizure frequency per 28 days during double -blind treatment will be tested first. If this test is significant at 0.05 level, then the 50% responder rate in the Maintenance Period for drop seizures will be tested. If this is significant then the 50% responder rate in the Maintenance Period for total seizures will be tested. All tests will be at a 2 -sided 0.05 significance level.

The same ANCOVA model employed for the primary efficacy variable will be employed to analyze percentage change from baseline in total seizures.

50% responder rates will be analyzed using the Cochran-Mantel-Haenszel (CMH) test, adjusting for region (Asia/Pacific, Europe, North America) and age group (2-<12 years, >=12 years). The homogeneity of the odds ratios will be checked across strata. For subjects who discontinue the study with less than 8 weeks of seizure data in the Maintenance Period, the last 8 weeks of data after the first dose (or entire double-blind treatment duration if <8 weeks of data are available) will be used in lieu of Maintenance Period.

Sensitivity analyses of the key secondary endpoints will be performed in the PP and ITT populations.

The primary and key secondary efficacy endpoints will be summarized by age group. 75% responder rate and seizure-freedom rate in drop and total seizures will be analysed by treatment group in the Maintenance-LOCF Period.

Percent change from baseline in non-drop seizures will be analysed similarly to drop and total seizures.

Summaries of the 50%, 75% and seizure freedom rates in non-drop seizures will also be produced. Seizure freedom is defined as being seizure free during the maintenance period and completing the core study.

The other secondary efficacy endpoint of Physicians' global evaluations over time will be analyzed using the CMH test.

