9.3.1 Inclusion Criteria

Subjects must meet all of the following criteria to be included in this study:

1. Subjects must have diagnosis of LGS as evidenced by:
 - a. More than one type of generalized seizures, including drop seizures (atonic, tonic, or myoclonic) for at least 6 months before Visit 1

- b. An EEG reporting diagnostic criteria for LGS at some point in their history (abnormal background activity accompanied by slow, spike and wave pattern < 2.5 Hz)
2. Subjects must be at least 2 years old at the time of consent/assent
3. Subjects must have been <11 years old at the onset of LGS
4. Subjects must have experienced an average of at least 2 drop seizures per week in the 4-week Baseline Period preceding randomization; the Baseline Period within the Prerandomization Phase is (minimum) 4 weeks. (revised per Amendment 04)
5. Subjects must have been receiving 1 to 4 concomitant AEDs at a stable dose for at least 30 days before Visit 1 (vagal nerve stimulation [VNS] and ketogenic diet do not count as an AED). Use of cannabidiol (CBD) products is allowed and is counted as one of the 4 maximum allowed concomitant AEDs. CBD dose and product must have remained stable for at least 30 days before Visit 1 and is to remain the same throughout the course of the Core Study. (revised per Amendment 04)
6. In the investigator's opinion, parents or caregivers must be able to keep accurate seizure diaries
7. Body weight at least 8 kg

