5.1.2 Secondary Endpoints

The following key secondary endpoints will be evaluated sequentially using the FAS:

1. Median percent change in total seizure frequency per 28 days during double –blind treatment (Titration Period and Maintenance Period) relative to the Prerandomization Phase.
2. The 50% responder rate in the Maintenance Period of the double-blind treatment relative to the Prerandomization Phase for drop seizures
3. The 50% responder rate in the Maintenance Period of the double-blind treatment relative to the Prerandomization Phase for total seizures.

Other secondary endpoints are:

4. Median percent change in non-drop seizure frequency per 28 days during double-blind treatment (Titration Period and Maintenance Period) relative to the Prerandomization Phase
5. Proportion of subjects with 75%, and 100% responder rates for drop, non -drop, and total seizures in the Maintenance Period relative to the Prerandomization Phase
6. Proportion of subjects with 50% responder rate in the Maintenance Period of the double-blind treatment relative to the Prerandomization Phase for non-drop seizures

7. Physicians' global evaluation of the subject's overall changes in symptoms (using a 7-point Likert scale with 1=very much improved and 7=very much worse) at the end of the double-blind treatment
8. Incidence of adverse events (AEs) and serious adverse events (SAEs), changes in clinical laboratory values, and vital signs
9. Model-derived average perampanel concentrations at steady state ($C_{av,ss}$) during the Maintenance Period of the Core Study

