5.2 CCI CCI STUDY SUBJECTS

5.2.1 Definitions of Analysis Sets

The **Safety Analysis Set (SAS)** is the group of subjects who received at least one dose of study drug and had at least one post-dose safety assessment.

The **Full Analysis Set (FAS)** is the group of randomized subjects who received at least one dose of study drug and had at least one post-dose seizure measurement.

The **Per Protocol Analysis Set (PP)** is the group of subjects who sufficiently complied with the protocol. Details of the evaluability criteria are given in Section 5.2.3.

The **Pharmacokinetic Analysis Set** is the group of subjects who received perampanel and had at least one quantifiable perampanel concentration during the Maintenance Period of the Core Study and adequately documented dosing history.

The **PK/PD analysis** set is the group of subjects who received perampanel or placebo who had seizure frequency data with documented dosing history. Subjects who received perampanel should have at least one quantifiable perampanel concentration as per the PK analysis set.

The **Intention to Treat Analysis Set (ITT)** is the group of randomized subjects who received at least one dose of study drug.

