5.3.1 Pre-Perampanel Baseline Analysis

The following analyses will be conducted for drop, non-drop and total seizures using the Full Analysis Set (Extension):

- Median percentage change in seizure frequency per 28 days from baseline over the entire perampanel treatment duration.

- Proportion of subjects with $\geq 50\%$, $\geq 75\%$, and 100% response for the perampanel treatment duration.

Efficacy endpoints will be summarised in 13-week intervals and overall.

For summaries by 13-week intervals a subject needs at least 1 day of seizure frequency data in a 13-week interval to be included in the summary for the overall perampanel treatment duration. To be counted as seizure-free, they would need to have completed the time interval.

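### Core SAP 5.4.2 defines non-drop seizure freedom without reference to baseline, so a completer who had no non-drop seizures at entry can count as a treatment success

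*SAP*

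**What the plan says.** Core SAP 5.1.2, item 5, lists 75% and 100% responder rates for drop, non-drop and total "seizures in the Maintenance Period relative to the Prerandomization Phase"; item 6 adds the 50% rate for non-drop seizures. Protocol 9.7.1.1 has the same endpoints and says they are to be summarized rather than analyzed statistically.

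Core SAP 5.4.2 puts this into operation: "Summaries of the 50%, 75% and seizure freedom rates in non-drop seizures will also be produced". It then gives the rule: "Seizure freedom is defined as being seizure free during the maintenance period and completing the core study". Those are the only two conditions. The same section has non-drop percent change analyzed in the manner used for drop and total seizures.

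On entry, Protocol 9.3.1 sets a minimum count for one kind of seizure: "Subjects must have experienced an average of at least 2 drop seizures per week in the 4-week Baseline Period preceding randomization". The only requirement on seizure type is "More than one type of generalized seizures, including drop seizures (atonic, tonic, or myoclonic) for at least 6 months before Visit 1". The Full Analysis Set (SAP 5.2.1) "is the group of randomized subjects who received at least one dose of study drug and had at least one post-dose seizure measurement"; it carries no non-drop condition, and no narrower set is named for the non-drop summaries. No section of the Core SAP or the protocol says what to do when the baseline non-drop frequency is zero.

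**The concern.** A 100% responder is someone whose seizures stopped. A subject who had none to begin with cannot respond, yet the wording in 5.4.2 admits that subject as a success on completing the Core Study without a non-drop seizure in maintenance. Three things follow if such subjects are present and are counted.

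- The non-drop freedom rate partly reports a feature of the subjects at entry rather than an outcome of treatment.
- The three non-drop rates stop being nested. The 100% rate can contain subjects who cannot appear in the 50% or 75% rate.
- A chance difference between arms in the number of such subjects can add to, or hide, a difference in the reported rates.

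Non-drop responder rates are a stated objective (secondary objective 5), and SAP 5.3.4 repeats the summaries by age group, where numbers are smaller.

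**Working it through.** **Can a zero baseline arise?** Criterion 4 secures drop seizures, and therefore total seizures, at baseline. Criterion 1 is a history of more than one generalized type over at least 6 months. It could be met by two drop types, or by a non-drop type that happens not to occur in the 4- to 8-week diary. Under SAP 8.1 a diary day is valid if any one seizure type has a positive count. A diary holding only drop seizures therefore gives an observed non-drop baseline of zero, not a missing one.

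**What happens to that subject?** Percent change divides by zero, so it and 50% or 75% response are undefined. Seizure freedom under 5.4.2 is defined and can be met.

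**Size.** The plan gives no expected rate for this endpoint, so there is no figure to reproduce. Let

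- q = share of subjects with zero baseline non-drop seizures;
- c = share of those who complete and stay free of non-drop seizures in maintenance;
- p = true freedom rate among subjects with baseline non-drop seizures.

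Reported rate = q × c + (1 - q) × p. It exceeds p whenever q > 0 and c > p.

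None of q, c and p is in the documents. Assume c = 90% in both arms, p = 5% on placebo and p = 10% on perampanel. At q = 10%, placebo is 0.10 × 0.90 + 0.90 × 0.05 = 13.5%, and perampanel is 0.10 × 0.90 + 0.90 × 0.10 = 18.0%.

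| q | Zero-baseline subjects per 71 | Placebo (true 5%) | Perampanel (true 10%) | Difference (true 5.0 points) |
|---|---|---|---|---|
| 5% | 3.6 | 9.3% | 14.0% | 4.8 |
| 10% | 7.1 | 13.5% | 18.0% | 4.5 |
| 20% | 14.2 | 22.0% | 26.0% | 4.0 |
| 30% | 21.3 | 30.5% | 34.0% | 3.5 |

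The rise in each arm is q × (c - p): from 0.05 × 0.80 = 4.0 points to 0.30 × 0.85 = 25.5 points over this range. At q = 10%, c = 80% gives 12.5% and 17.0%, and c = 100% gives 14.5% and 19.0%. If only half of the zero-baseline subjects complete and stay free (c = 50%), the rates are 0.05 + 0.045 = 9.5% and 0.05 + 0.09 = 14.0%.

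**Between-arm difference.** With equal c, the expected difference is (1 - q) times the true one. If c differs by arm, for instance through completion, a term q × (difference in c) is added.

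**Chance imbalance.** Randomization balances q only on average. At q = 10% and 71 per arm, the standard deviation of the between-arm difference in zero-baseline share is about √(2 × 0.10 × 0.90 / 71) = 5.0 points, or about 3.6 subjects. Each point of excess in one arm moves that arm's rate by c - p, here 0.80 to 0.85 of a point. One standard deviation therefore shifts the difference by about 4 points, against an assumed true difference of 5.

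**Restricting the denominator** to subjects with baseline non-drop frequency above zero returns p itself in each arm.

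**The case against.** The strongest reply is that 5.4.2 should not be read alone. SAP 5.1.2 ties the 100% rate to the Prerandomization Phase, and SAP section 7 says nothing has changed from the protocol. On that reading 5.4.2 adds a completion condition to a baseline-linked endpoint, and a zero-baseline subject is not a responder. Derivation rules and table shells are in separate documents (SAP sections 9 and 11) and may already restrict the denominator. This is a fair account of what may be intended. It does not remove the problem, because the explicit rule in 5.4.2 omits the baseline link and a programmer following it would count the subject.

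Zero baselines may also be rare. The natural reading of criterion 1 is drop seizures plus some other type. SAP 5.4.1 limits myoclonic drop seizures to those with a fall, so myoclonic seizures without one would seem to be non-drop. This stands: the documents do not show how often the case occurs, or that it occurs at all.

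A reader might infer that the rule favors perampanel. It does not: with 1:1 allocation and similar c, both arms are expected to rise and the difference to shrink.

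A reader might also infer that the Extension SAP has the same defect. It does not contain this definition. Its section 5.3.1 speaks of response from baseline and adds only an interval-completion condition for seizure freedom. For former placebo subjects the baseline also includes Core Study diary data, which makes a zero less likely. All that is missing there is a stated denominator.

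**Conclusion.** The concern holds as a minor one. As written, the seizure-freedom rule in Core SAP 5.4.2 departs from the listed endpoint and gives a wrong classification for any completer with no non-drop seizures at baseline or in maintenance. The same gap leaves non-drop percent change and 50% and 75% response undefined for every zero-baseline subject.

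The direction of the effect is clear if c exceeds p; its size in this trial cannot be computed. The figures above rest on assumed q, c and p, and on the planned 71 per arm. They do not show that the reported rate is in fact inflated, only that it would be if such subjects exist and are left in the denominator.

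Drop and total seizures are not affected, because criterion 4 gives both a non-zero baseline. The endpoint is summarized and lies outside the testing sequence in SAP 5.3.3, so the primary and key secondary tests, type I error and sample size are unchanged.

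**What to change.** In Core SAP 5.4.2, restrict non-drop percent change and the non-drop 50%, 75% and 100% rates to FAS subjects with a baseline non-drop frequency above zero. Report that n per arm. List the zero-baseline subjects separately by arm, with the number who developed non-drop seizures on treatment.

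For consistency, state the same denominator in Extension SAP 5.3.1, where the terms are already linked to baseline.

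The cost is a sentence or two and a denominator in the table shells. No new data are needed. The downside is a somewhat smaller n for a descriptive endpoint.

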9.7.1.1 Study Endpoints

PRIMARY ENDPOINTS

The primary efficacy endpoint will be the median percent change in drop seizure frequency per 28 days during double-blind treatment (Titration Period and Maintenance Period) relative to the Prerandomization Phase in the Full Analysis Set (FAS).

SECONDARY ENDPOINTS

The following key secondary endpoints will be evaluated sequentially using the FAS:

1. Median percent change in total seizure frequency per 28 days during double-blind treatment (Titration Period and Maintenance Period) relative to the Prerandomization Phase.
2. The 50% responder rate in the Maintenance Period of the double-blind treatment relative to the Prerandomization Phase for drop seizures
3. The 50% responder rate in the Maintenance Period of the double-blind treatment relative to the Prerandomization Phase for total seizures.

Other secondary endpoints are as follows. They will not be analyzed statistically but will be summarized. (revised per Amendment 01):

4. Median percent change in non-drop seizure frequency per 28 days during double-blind treatment (Titration Period and Maintenance Period) relative to the Prerandomization Phase
5. Proportion of subjects with 75%, and 100% responder rates for drop, non-drop, and total seizures in the Maintenance Period relative to the Prerandomization Phase
6. Proportion of subjects with 50% responder rate in the Maintenance Period of the double-blind treatment relative to the Prerandomization Phase for non-drop seizures
7. Physicians' global evaluation of the subject's overall changes in symptoms (using a 7-point Likert scale with 1=very much improved and 7=very much worse) at the end of the double-blind treatment.
8. Incidence of AEs and SAEs, changes in clinical laboratory values, and vital signs
9. Model-derived average perampanel concentrations at steady state ($C_{av,ss}$) during the Maintenance Period of the Core Study

EXPLORATORY ENDPOINTS

CCI

CCI

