9.7.1.6 Efficacy Analyses

PRIMARY EFFICACY ANALYSIS

The analysis of the primary endpoint, percentage change in drop seizure per 28 days in the FAS, will be conducted using rank analysis of covariance (ANCOVA), with ranked percentage change from baseline in drop seizures per 28 days as the dependent variable and treatment, age group, region, and ranked baseline drop seizure rate per 28 days as the independent variables. Seizure frequency will be based on the number of drop seizures per 28 days, calculated as the number of

drop seizures over the entire time interval divided by the number of days in the interval and multiplied by 28.

Treatment effect in different age groups will be investigated.

A 5% (2-sided) level of significance will be used for all analyses.

SECONDARY EFFICACY ANALYSIS

The 3 key secondary efficacy endpoints will proceed in a sequential manner.

[figure not shown]
Median percent change in total seizure frequency per 28 days during double-blind treatment will be tested first. If this test is significant at 0.05 level, then the 50% responder rate in the Maintenance Period for drop seizures will be tested. If this is significant then the 50% responder rate in the Maintenance Period for total seizures will be tested. All tests will be at a 2-sided 5% significance level.

50% responder rates will be analyzed using the Cochran-Mantel-Haenszel (CMH) test, adjusting for region and age group. For subjects who discontinue the study with less than 8 weeks of seizure data in the Maintenance Period, the last 8 weeks of data after the first dose (or entire double-blind treatment duration if <8 weeks of data are available) will be used in lieu of Maintenance Period. The treatment effect will be assessed using odds ratio. The common odds ratio and 95% CI as well as response rate from each treatment group will be presented. (revised per Amendment 01)

The same ANCOVA model employed for the primary efficacy variable will be employed to analyze percentage change from baseline in total seizures.

Physicians' global evaluations over time will be analyzed using the CMH test.

EXPLORATORY EFFICACY ANALYSIS

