5.3.5 Handling of Missing Data, Drop-outs, and Outliers

5.3.5.1 Efficacy

For the last observation carried forward (LOCF) analyses, such as “Maintenance-LOCF” analyses of percent change and responder rate, if the overall duration of the Maintenance Period is less than 8 weeks, the diary data up to the last 8 weeks during the Titration and Maintenance Periods combined will be used to calculate the seizure frequency per 28 days for Maintenance-LOCF.

For the ITT analysis, subjects with no post-baseline efficacy data will have their baseline observation carried forward.

Since data is rank transformed prior to analysis, outliers will have no effect on the primary analysis.

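### SAP 5.4.2 scores a dropout on seizure freedom in two incompatible ways: by Maintenance-LOCF, or as a failure because the Core Study was not completed

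*SAP*

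**What the plan says.** - **Endpoint lists.** Endpoint 5 in Protocol 9.7.1.1, one of the other secondary endpoints, reads: "Proportion of subjects with 75%, and 100% responder rates for drop, non-drop, and total seizures in the Maintenance Period relative to the Prerandomization Phase". Core Study SAP 5.1.2 repeats it. Neither sets a completion condition or says how a dropout is scored on the 100% rate.
- **Status.** Protocol 9.7.1.1 says the other secondary endpoints are summarised and not tested. They lie outside the sequential testing in Core Study SAP 5.3.3.
- **Protocol dropout rule.** Protocol 9.7.1.6 has a substitution that begins "For subjects who discontinue the study with less than 8 weeks of seizure data in the Maintenance Period, the last 8 weeks". It directly follows the sentence on the 50% responder rates and is not extended to the 75% or 100% rates.
- **SAP window.** Core Study SAP 5.4.2: "75% responder rate and seizure-freedom rate in drop and total seizures will be analysed by treatment group in the Maintenance-LOCF Period". SAP 5.3.5.1 explains the window for a Maintenance Period under 8 weeks long: "the diary data up to the last 8 weeks during the Titration and Maintenance Periods combined will be used to calculate the seizure frequency".
- **SAP definition.** Three sentences later, after two sentences on non-drop seizures, SAP 5.4.2 adds: "Seizure freedom is defined as being seizure free during the maintenance period and completing the core study".
- **Changes.** Core Study SAP 7 declares no change in statistical methods from the protocol.

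**The concern.** The two SAP sentences disagree about the same people. A subject who leaves early and has no seizures in the LOCF window counts as a success under the first sentence and a failure under the second. The LOCF window has no minimum length. SAP 5.4.1, describing the same window for percent change, falls back on whatever Titration and Maintenance data exist, and the FAS needs only one post-dose seizure measurement (SAP 5.2.1). Someone who stops after a few quiet days of Titration could therefore be reported as 100% seizure free.

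The scope of the definition is also unclear. Its wording is general, but it closes a paragraph about non-drop seizures. Read as general, it overrides the LOCF sentence. Read as non-drop only, it leaves drop and total seizures on a more lenient rule than non-drop seizures, with no reason given.

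What is at stake is how the seizure-free rate is reported, overall and in the age-group summaries of SAP 5.3.4, where denominators are smaller. Few subjects may be seizure free in a population entering with an average of at least 2 drop seizures a week, so a handful of reclassified dropouts could be a visible share of the count.

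**Working it through.** **1. Is there a planned figure to reproduce?** None is stated for seizure freedom. The nearest is the 97% power for the 50% drop-seizure responder rate (71 per arm, 20% versus 50%). With mean proportion 0.35:

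z = [0.30 - 1.96 x sqrt(2 x 0.35 x 0.65 / 71)] / sqrt[(0.2 x 0.8 + 0.5 x 0.5) / 71] = (0.300 - 0.157) / 0.0760 = 1.88, so power = 97.0%.

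This confirms 71 as the planning denominator and has no other bearing on the point.

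**2. Do the two SAP rules give different answers?** Take a 6-week Titration (weeks 1-6) and a 12-week Maintenance (weeks 7-18), and apply each rule to hypothetical subjects:

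| Subject | LOCF window | Maintenance-LOCF | Completion definition |
|---|---|---|---|
| A: stops at week 16, seizure free through 10 Maintenance weeks | weeks 7-16 | seizure free | not |
| B: stops at week 10, seizure free from week 3 | weeks 3-10 | seizure free | not |
| C: stops at week 10, seizures through week 6, none after | weeks 3-10 | not | not |
| D: stops at week 5, in Titration, no seizures at all | weeks 1-5 | seizure free | not |
| E: completer, seizure free in Maintenance | weeks 7-18 | seizure free | seizure free |

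A, B and D change status; E does not. Among these cases only dropouts are affected.

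**3. Can both sentences operate together?** LOCF is triggered by under 8 weeks (56 days) of Maintenance. Protocol Table 5 puts Visit 5 at Day 43 and Visit 7 at Day 127, each with a window of 6 days either way. The shortest in-window Maintenance Period is 127 - 43 - 12 = 72 days. A subject who completes on treatment within the visit windows therefore never triggers LOCF, and under the completion definition a dropout can never be a success. For seizure freedom the LOCF sentence then does nothing.

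**4. How large is it?** One subject is 1/71 = 1.4 percentage points of an arm. The documents give no dropout rate and no seizure-free rate, so both of the following are assumptions:

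- d = share of an arm that drops out, 5% to 20%;
- s = share of those dropouts seizure free in the window used, 5% to 30%.

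Subjects changing status = 71 x d x s; points = 100 x d x s.

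| d | s | Subjects per arm | Points |
|---|---|---|---|
| 5% | 5% | 0.18 | 0.25 |
| 10% | 10% | 0.71 | 1.0 |
| 10% | 20% | 1.42 | 2.0 |
| 20% | 10% | 1.42 | 2.0 |
| 20% | 30% | 4.26 | 6.0 |

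**5. Is the upper end plausible?** Assume a constant Poisson rate at the entry minimum of 2 drop seizures a week, with no treatment effect. The chance of none in w weeks is exp(-2w): 13.5% at 1 week, 1.8% at 2 weeks, 0.03% at 4 weeks. A 30% chance needs w = ln(1/0.30)/2 = 0.60 weeks, about 4 days. A 5% chance needs w = ln(20)/2 = 1.50 weeks, about 10 days. Treatment benefit or clustering would raise these chances; a baseline above the minimum, or counting all seizures, would lower them. The top of the range therefore needs very short windows or a real effect in subjects who nevertheless stopped.

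**The case against.** The strongest reply is that the SAP already contains a controlling definition. The sentence names no seizure type, so it can be read as covering all three. Every dropout is then a failure, and the Maintenance-LOCF label is simply shared with the 75% rate and redundant for seizure freedom. That reading is reasonable and is the one the fix adopts. It is not the only reading: the LOCF sentence expressly assigns the drop and total seizure-freedom rates to that window, and the definition sits with the non-drop text. A programmer could follow either.

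A reader might go further and infer three rival rules, with the protocol's Maintenance-only wording as the third. The documents do not support that. The protocol names the period and is silent on dropouts for this rate. Scoring subject C a success on four available Maintenance weeks would read a rule into that silence, and subject D would have no Maintenance days to score. Protocol 9.7 leaves analysis detail to the SAP, so filling the gap is not plainly a departure, and the statement in SAP 7 is at most incomplete.

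Two further points stand. The endpoint is descriptive under the protocol, although secondary objectives 2 and 3 speak of showing superiority on the 100% rate and SAP 5.1.2 omits the sentence limiting other secondaries to summaries. Also, derivation rules and table shells are in separate documents (SAP 9 and 11), so the scoring actually programmed cannot be known from these texts.

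**Conclusion.** The point holds as an internal conflict in Core Study SAP 5.4.2: two stated rules give opposite scores for a dropout who is seizure free in the LOCF window. It is more than missing detail, because following the LOCF sentence literally counts short-exposure dropouts as seizure free.

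The consequence is modest: 1.4 points of a 71-subject arm per reclassified dropout, and roughly 0 to 4 subjects (0.25 to 6 points) under the assumed ranges, with the upper end unlikely unless windows are very short or treatment works well in those who stop. The primary analysis, the key secondary endpoints, type I error and the sample size are unaffected.

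A reader might also infer that the choice of rule biases the comparison between arms. That would require seizure-free dropout to differ by arm, and the documents give no dropout rates by arm, so it remains a possibility only. Equating the 100% responder with seizure freedom is itself an inference. It is a safe one, because SAP 5.3.4 and 5.4.2 list seizure freedom beside the 50% and 75% rates where the objectives list 100%.

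**What to change.** State one rule in Core Study SAP 5.1.2 and apply it to drop, non-drop and total seizures. A subject is seizure free if there are zero seizures of that type on the valid days of the actual Maintenance Period and the Core Study was completed. All other FAS subjects count as not seizure free. This is the SAP's own definition with its scope and denominator made explicit.

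In SAP 5.4.2, remove seizure freedom from the Maintenance-LOCF sentence and keep LOCF there for the 75% rate. Leave the existing 8-week substitution for the 50% responder rates as it is. Record the completion condition in SAP 7, since the protocol endpoint does not contain it.

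The cost is SAP wording, with matching checks of the programming specifications and table shells. The seizure-free rates become slightly less favourable, because no dropout can count as seizure free. It is best settled before unblinding.
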